8 STATISTICAL METHODS

The Biostatistics groups of Clinical Development at Johnson and Johnson Global Surgery Group will be responsible for the overall analysis of data from this protocol. The detailed Statistical Analysis Plan (SAP) will be based on and will supplement the statistical design and analysis described in this section.

8.1 Sample Size Determination

The sample size required for the trial is 42 randomized Subjects. This sample size is considered adequate by EMA Paediatric Investigation Plan to summarize the data descriptively. The continuous data will be summarized by number of subjects, mean, median and standard deviation (SD).

8.2 Planned Analyses

8.2.1 Analysis Sets

In all cases, treatment allocation will be based on randomisation. If more than two subjects are mis-randomized, then an additional analysis based on treatment received will be used for confirmatory analyses for all effectiveness endpoints.

Three analysis sets are defined:

- The Safety Set will contain all subjects who received treatment.
- The Full Analysis Set (FAS) will contain all randomized subjects (equivalent to the Intent-to-Treat [ITT] set).
- The Per Protocol Set will contain subjects in the FAS who have no major protocol deviations affecting the primary endpoint (these will be agreed before database lock).

8.3 Effectiveness

The following will be analyzed using the FAS and Per Protocol Set:

- Proportion of success (intraoperative watertight closure) in the treatment of intraoperative CSF leakage defined as no CSF leakage from dural repair intraoperatively, during Valsalva maneuver 20-25 cm H₂O for 5-10 seconds.

The primary analysis will use the FAS for proportion of successes. The Per Protocol analysis will be considered confirmatory.

8.3.1 Methods of Analysis

The continuous data will be summarized by number of subjects, mean, standard deviation (SD), minimum and median and maximum. The categorical data will be summarized by frequency along with associated percentages. In addition, two sided 95% CI will be reported for ratio of the proportion of success in the EVICEL treated subjects/the proportion of success in Control subjects

8.4 Safety/Secondary Endpoints

8.4.1 Safety/Secondary Endpoints Variables/Criteria

The following will be summarized using the Safety Set:

Safety and tolerability assessments:

- Adverse events

- Laboratory tests
- Incidence of CSF leakage within 5 days (\pm 2 days) post-operatively.
- Incidence of CSF leakage within 30 days (\pm 3 days) post operatively.
- Incidence of adverse events (including CSF leaks, pseudomeningocele formation, etc.)
- Incidence of surgical site infections (SSI) according to National Healthcare Safety Network (NHSN) criteria within 30 days (\pm 3 days) post-operatively.

8.4.2 Methods of Analysis

Adverse events will be summarised descriptively by the treatment received, using Medical Dictionary for Regulatory Activities (MedDRA) terminology. Coagulation parameters (baseline and post-surgery samples) will use SI units.

Laboratory values will be reported in International System (SI) units. Values and changes from baseline will be listed but not summarised. Clinically significant changes will be reported as part of the AE summary.

8.5 Handling of Missing Data

It is not anticipated that there will be any data missing for treated subjects for the primary endpoint, but if there is, missing data will be considered failures for the primary analysis. Confirmatory analyses will be performed considering missing data as successes, and also, worst-case (with missing data for the EVICEL® group considered failures and missing data for the Control group considered successes).

Analyses of secondary endpoints consider missing data as failures.

9 ADVERSE EVENTS

9.1 Adverse Event

An adverse event means any untoward medical occurrence associated with the use of a drug in humans, whether or not considered drug related. An adverse event (also referred to as an adverse experience) can be any unfavorable and unintended sign, symptom, or disease temporally associated with the use of a drug, without any judgment about causality. Since post operative pain is an expected outcome of this type of surgery, for purposes of this study, only exacerbations of expected post operative pain based on the Investigator's judgment should be reported as an AE.

The Investigator may also need to consider whether an adverse event is attributable to the application device, based on any of the following:

- Resulting from insufficiencies or inadequacies in the IFU
- In the actual use of the application device, tips or regulator
- The result of user error

9.2 Suspected adverse reaction

A suspected adverse reaction means any adverse event for which there is a reasonable possibility that the drug caused the adverse event. Reasonable possibility means there is evidence to suggest a causal relationship between the drug and the adverse event. A suspected adverse reaction implies a lesser degree of certainty about causality than adverse reaction.

9.3 Adverse reaction

An adverse reaction means any adverse event caused by a drug. Adverse reactions are a subset of all suspected adverse reactions for which there is reason to conclude that the drug caused the event.

9.4 Serious Adverse Event

A "serious" adverse event (SAE) is any untoward medical occurrence that, in the view of either the investigator or sponsor, it:

- Results in death;
- Is considered to be life-threatening;
- Requires inpatient hospitalization or prolongation of existing hospitalization;
- Results in persistent or significant disability, incapacity or substantial disruption of the ability to conduct normal life functions;
- Results in a congenital anomaly or birth defect;
- Is an important medical event that may not result in death, be life-threatening, or require hospitalization but may be considered serious when, based upon appropriate medical judgment, they may jeopardize the patient or subject and may require medical or surgical intervention to prevent one of the outcomes listed in this definition.

9.4.1 Life threatening

Life threatening refers to an adverse event or suspected adverse reaction in which, in the view of the investigator or sponsor, the subject was at immediate risk of death at the time of the event; it does not include an event that might have caused death if it were more severe.

9.4.2 Hospitalizations

Any event requiring inpatient hospitalization (or prolongation of hospitalization) that occurs during the course of a subject's participation in a clinical study must be reported as a serious adverse event, except hospitalizations for the following:

- Social reasons in absence of an adverse event;
- Surgery or procedure planned before entry into the study (must be documented in the CRF).

9.4.3 Unexpected

An adverse event or suspected adverse reaction is considered "unexpected" if it is not listed in the investigator brochure or is not listed at the specificity or severity that has been observed; or, though they are mentioned as occurring with a class of drugs or as anticipated from the pharmacological properties of the drug, they are not specifically mentioned as occurring with the particular drug under investigation.

9.4.4 Suspected Unexpected Serious Adverse Reaction (SUSAR)

A suspected unexpected serious adverse reaction (SUSAR) is a suspected adverse reaction that is both serious and unexpected.

9.5 Relationship

The relationship of the investigational product to an adverse event must be determined using the following classification based on the information on the Investigator Brochure:

None: No relationship with investigational product.

Possible: Reasonable possibility that the event was caused by the investigational product.

Related: The event was certainly or probably caused by the investigational product.

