9.7 Collection of Adverse Events

AEs will be recorded as they are reported, whether spontaneously volunteered or in response to questioning about well-being. AEs will be collected from the point of randomization during the surgical procedure, throughout the hospital admission, and until completion of the 30-day follow-up visit.

All AEs will be documented in the subject's source documents (e.g. medical records) and eCRF. All AEs will be followed until completion of the 30-day follow-up visit or until a stable resolution, whichever is sooner.

Details of all AEs occurring during the study must be recorded on the AE form with the following information:

- Description of the event
- Dates of onset and resolution
- Severity
- Action taken
- Outcome
- Relationship to investigational product
- Whether the AE is serious or not

Expectedness of an SAE will be defined based on whether the specificity or severity of which is not consistent with the current investigator brochure.

Other: The investigator may also need to consider whether an event is attributable to the investigational product, based on insufficiencies or inadequacies in the instructions for use or as a result of user error. The investigator must contact the Sponsor should this occur.

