2.2.2	5-day (± 2 days) and 30-day (± 3 days) follow-up assessments – FAS	Indication of re-hospitalizations since previous study visit, indication of surgical procedures since previous study visit, indication of relevant changes in medical history since screening, presence of clinically significant changes to subject since baseline, surgical site assessment, including presence of infection (brain abscess, meningitis, and/or surgical site infection – superficial incisional, deep incisional and/or organ-space), hematoma (intradural, extradural, and/or subcutaneous), pseudomeningocele, and other surgical site experience, wound healing assessment, CSF leak determination - all (d)	G2
3	Safety data		
3.1	Adverse Events		
3.1.1	Number of subjects experiencing any during/post treatment AE by category – Safety analysis set		AS
3.1.2	Adverse events (during/post treatment) by subject, MedDRA preferred term and system organ class – Safety analysis set		AM
3.1.3	Summary of during/post treatment adverse events by subject and coded terms, preferred terms occurring in $\geq 5\%$ of subjects – Safety analysis set		AM
3.1.4	Summary of during/post treatment serious adverse events by subject and coded terms – Safety analysis set	Includes adverse events for which the answer for CRF question “Serious?” in the CRF is “Yes”	AM
3.1.5	Summary of during/post treatment surgical procedure related (possibly, definitely) adverse events by subject and coded terms – Safety analysis set	Includes adverse events for which the answer for CRF item “Relationship to surgical procedure” is “Possibly related” or “Related”.	AM
3.1.6	Summary of during/post treatment study treatment related (possibly, definitely) adverse events by patient and coded terms – Safety analysis set	Includes adverse events for which the answer for CRF item “Relationship to study treatment” is “Possibly related” or “Related”.	AM

No	Title of table/figure	Notes	Shell ¹
3.2	Laboratory data	Reported in SI units	
3.2.1	Laboratory data: Complete Blood Count - Safety analysis set	At baseline and at 5-day follow-up	L
3.2.2	Laboratory data: White Blood Cell Differential - Safety analysis set	At baseline and at 5-day follow-up	L
3.2.3	Laboratory data: Creatinine, Liver Function Test and Electrolytes - Safety analysis set	At baseline and at 5-day follow-up	L
3.3	Other safety data		

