	DYSPEPSIA	9 (9.9%)	9 (9.9%)	9 (9.9%)
	GASTRIC ULCER	9 (9.9%)	9 (9.9%)	9 (9.9%)

[If any Ethicon specific codes used these will be indicated with an '*']
 [FIRST PAGE ONLY SHOWN]

Study: [Short title and number]
 Program: t_all.sas Run date: 12SEP06 Time: 08:40
 CONFIDENTIAL Programmer: << name >> Program status: VALIDATED Data Status: LOCKED ON DDDMM20YY
 Source: Listing 16.2.x.x
 ^: MedDRA version x.x

EXAMPLE TABLE AS (Adverse Event Overall Summary)

Table 14.3.1.1
Number of patients experiencing any during/post treatment AE by category
Safety analysis set

Variable	Category /Statistic	Ethicon trt (n=99)		Comparitor trt (n=99)		Total (n=999)	
Individual AE	(^)	Yes	999 (na)	999 (na)	999 (na)	999 (na)	999 (na)
Individual SAE	(^)	Yes	999 (na)	999 (na)	999 (na)	999 (na)	999 (na)
At least 1	(\\$)	Yes	99 (99.9%)	99 (99.9%)	99 (99.9%)	99 (99.9%)	99 (99.9%)
Serious	(\\$)	Yes	99 (99.9%)	99 (99.9%)	99 (99.9%)	99 (99.9%)	99 (99.9%)
Severe	(\\$)	Yes	99 (99.9%)	99 (99.9%)	99 (99.9%)	99 (99.9%)	99 (99.9%)
Action taken	(%\\$)	Yes	99 (99.9%)	99 (99.9%)	99 (99.9%)	99 (99.9%)	99 (99.9%)
Related	(+\\$)	Yes	9 (99.9%)	9 (9.9%)	9 (9.9%)	9 (9.9%)	9 (9.9%)

[Categories as AE page in CRF, definition of '+' as in SAP]

Study: [Short title and number]
 Program: t_all.sas Run date: 12SEP06 Time: 08:40
 CONFIDENTIAL Programmer: <> name >> Program status: VALIDATED Data Status: LOCKED ON DDMM20YY
 Source: Listing 16.2.x.x
 ^: total number of AEs
 \$: Number of patients with at least 1 AE in this category
 %: Medical, surgical or other action taken
 +: Possibly related, related or related to application device

EXAMPLE TABLE DC (Discrete data- change)

Table 14.x.x.x
 XXXXXXXXXXXX
 xxxx analysis set

Variable	Category	Missing	Baseline					TOTAL
			Category 1					
Proc, Variable, Visit xx	Missing	9 (9.9%)	9 (9.9%)	9 (9.9%)	9 (9.9%)	9 (9.9%)	9 (9.9%)	9 (9.9%)
	Category 1	9 (9.9%)	9 (9.9%)	9 (9.9%)	9 (9.9%)	9 (9.9%)	9 (9.9%)	9 (9.9%)
	Category 2	9 (9.9%)	9 (9.9%)	9 (9.9%)	9 (9.9%)	9 (9.9%)	9 (9.9%)	9 (9.9%)
	Category 3	9 (9.9%)	9 (9.9%)	9 (9.9%)	9 (9.9%)	9 (9.9%)	9 (9.9%)	9 (9.9%)
	Category 4	9 (9.9%)	9 (9.9%)	9 (9.9%)	9 (9.9%)	9 (9.9%)	9 (9.9%)	9 (9.9%)
	TOTAL	9 (9.9%)	9 (9.9%)	9 (9.9%)	9 (9.9%)	9 (9.9%)	9 (9.9%)	9 (9.9%)
Proc, Variable, Visit xx	Improving^							9 (9.9%)

[Improving should not be given if it is not clear what improvement is.]

[For two treatment studies include variable name in the heading, and in the variable column add treatment]

Study: [Short title and number]

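### The protocol rates adverse-event causality only against EVICEL, while the SAP tabulates treatment-related events by arm from a CRF item left undefined for Control; taken literally, that table is zero in Control by construction

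*Protocol*

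**What the plan says.** **Protocol.** Section 9.5 sets the causality scale: "The relationship of the investigational product to an adverse event must be determined using the following classification", with the Investigator Brochure as its basis. The grades are None, Possible and Related, each worded by reference to the product; the lowest reads "None: No relationship with investigational product". Section 9.7 lists what the AE form must hold, and its only causality entry is "Relationship to investigational product". Section 9.1 adds that "The Investigator may also need to consider whether an adverse event is attributable to the application device". Neither 9.5 nor 9.7 provides a rating against the control sutures or against the operation.

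**SAP.** Section 10.2.2 plans two causality tables for the Safety set. Table 14.3.1.6 is titled "Summary of during/post treatment study treatment related (possibly, definitely) adverse events by patient and coded terms" and selects on a CRF item called *Relationship to study treatment*. Table 14.3.1.5 covers procedure-related events, with the note "Includes adverse events for which the answer for CRF item “Relationship to surgical procedure” is “Possibly related” or “Related". Both use shell AM, which has a column for each arm and a total. Shell AS has a by-arm row for related events, footnoted "Possibly related, related or related to application device". SAP section 9.4 groups AEs by treatment received and plans no inference. SAP section 4 records no change from the planned analysis.

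**The concern.** The two documents describe different ratings. The protocol asks whether EVICEL caused the event. The SAP assumes that sites were asked about study treatment and, separately, about surgery. Neither document says what study treatment means for a child given extra sutures.

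This matters because the related-event table is laid out as a comparison of arms. If sites follow Protocol 9.5, an event that the investigator blames on the additional suturing must still be graded None. The table can then show an excess on EVICEL when the two closure methods cause harm equally often. If instead some sites read the CRF item as covering sutures and others do not, one row mixes two definitions. With no test or interval planned, and investigators who know the allocation, readers would take the counts at face value.

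**Working it through.** The documents give no figure for related AEs, so there is nothing to reproduce. The check has two parts.

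**1. Can a Control child have a related event under the protocol's definition?**

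- Protocol section 6 separates EVICEL (6.1) from Control, which is additional sutures only (6.3).
- In Control, Protocol 7.1.3 requires the prepared EVICEL to be removed from the sterile field, and rescue after failure excludes EVICEL.
- AEs are summarised by treatment received (Protocol 8.4.2, SAP 9.4). A child allocated to Control but given EVICEL by mistake would therefore not be counted under Control.
- So the Control count of product-related events is zero by definition. Device-related events are likewise confined to EVICEL recipients.

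The labels also differ. The protocol uses Possible and Related, where Related means certainly or probably caused. The SAP selects on Possibly related and Related, and its table titles say possibly and definitely.

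**2. How far could the definition alone distort the table?**

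Inputs: 42 subjects at 2:1 (Protocol synopsis, SAP section 2), so 42 × 2/3 = 28 EVICEL and 42 × 1/3 = 14 Control. Let p be the proportion of children with an event truly caused by the closure method, equal in both arms. The documents do not give p; 5% to 30% is **assumed**.

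- EVICEL-only rating: P(at least one related on EVICEL, none on Control) = 1 − (1 − p)^28, because Control is fixed at zero.
- Symmetric rating: the same probability is [1 − (1 − p)^28] × (1 − p)^14.

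| p (assumed) | Expected subjects with a related event, symmetric rating (EVICEL, Control) | P(some vs none), EVICEL-only rating | (1 − p)^14 | P(some vs none), symmetric rating |
|---|---|---|---|---|
| 5% | 1.4, 0.7 | 0.762 | 0.488 | 0.762 × 0.488 = 0.37 |
| 10% | 2.8, 1.4 | 0.948 | 0.229 | 0.948 × 0.229 = 0.22 |
| 20% | 5.6, 2.8 | 0.998 | 0.044 | 0.998 × 0.044 = 0.04 |
| 30% | 8.4, 4.2 | >0.999 | 0.007 | about 0.007 |

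With no true difference, the definition raises the chance of this one-sided table from 37% to 76% at p = 5%, and from 22% to 95% at p = 10%. The symmetric column is the right baseline: with only 14 Control subjects, an empty Control cell is common even under fair rating when p is low.

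**The case against.** The strongest reply is that the zero is not established. The SAP names two CRF items. The one on surgical procedure applies equally to both arms, and the one on study treatment could be read to include sutures. The CRF was not available, so symmetric ratings may already be collected, and all sites complete common eCRFs. This stands as a limit on the claim: the zero follows only if the protocol's definition governs. It does not remove the conflict, because the protocol text that sites work from says investigational product and nothing reconciles the two.

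The second reply is that the shell AS footnote is template text. SAP Appendix 1 says that the shells show style and that footnotes will change to suit the study. That is fair, so the footnote is weak evidence on its own. Table 14.3.1.6, however, is in the SAP's own table list.

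A third reply is that rating against the product suits the protocol's definitions of adverse reaction and SUSAR. That is correct for expedited reporting, but it gives no reason to print a Control column.

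A reader might go further and infer that safety cannot be compared between the arms at all. The documents do not support that. The safety endpoints are incidence of AEs, CSF leakage and surgical site infection, and none depends on causality. Tables 14.3.1.1 (apart from any related row), 14.3.1.2 to 14.3.1.4 and 14.3.3 present AEs, serious AEs, leaks and infections by arm without a causality filter. Pseudomeningocele is in Table 14.2.2.2. A harm caused by extra suturing is therefore still counted.

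**Conclusion.** The concern holds for the treatment-related AE table and for any related row built on shell AS. Protocol 9.5 and 9.7 do not match the CRF items on which SAP Tables 14.3.1.5 and 14.3.1.6 rest, and study treatment is undefined for Control. Under the protocol's definition the Control column is a structural zero and the comparison is not interpretable.

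The size is illustrative. At an assumed equal true rate of 10% or 5%, a some-versus-none table appears in about 95% or 76% of trials, against about 22% or 37% under symmetric rating. This assumes a 28/14 split, independent subjects and literal use of Protocol 9.5.

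The all-AE, serious-AE, CSF-leak and infection summaries are unaffected. So is the procedure-related table, provided that item is on the CRF. The point is worth correcting because it could mislead and costs little to put right; it does not undermine the safety evaluation as a whole.

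**What to change.** Align Protocol 9.5 and 9.7, the CRF and the SAP:

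- Rate every AE in both arms, on one scale with one set of labels, for relationship to the surgical procedure and to the dural closure treatment received (EVICEL or additional sutures). Treatment received, rather than assigned, matches how AEs are summarised.
- Keep a causality judgement against EVICEL for SUSAR assessment.
- If relatedness to the application device is reported, give it a separate row for EVICEL only.
- Build Tables 14.3.1.5 and 14.3.1.6 and any related row on these ratings, and state the definition in SAP section 9.

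If the rating stays tied to EVICEL, print Table 14.3.1.6 and the related row for EVICEL only. Base between-arm safety comparisons on all AEs, serious AEs and, if that item is collected, procedure-related AEs.

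The cost is wording changes, at most one extra rating per AE and a small change to the shells. No visits or subjects are added. Causality judged by unblinded investigators stays subjective under either option, so the unfiltered AE tables should remain the main comparison.

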9.6 Severity

The following definitions should be used to determine the severity rating of all AEs:

Mild: Awareness of signs or symptoms, but these are easily tolerated and are transient and mildly irritating only. There is no loss of time from normal activities and symptoms do not require medication or a medical evaluation.

Moderate: Discomfort enough to cause interference with usual activities or require therapeutic intervention, such as concomitant medication.

Severe: Incapacity with inability to work or do usual activities.

9.7 Collection of Adverse Events

AEs will be recorded as they are reported, whether spontaneously volunteered or in response to questioning about well-being. AEs will be collected from the point of randomization during the surgical procedure, throughout the hospital admission, and until completion of the 30-day follow-up visit.

All AEs will be documented in the subject's source documents (e.g. medical records) and eCRF. All AEs will be followed until completion of the 30-day follow-up visit or until a stable resolution, whichever is sooner.

Details of all AEs occurring during the study must be recorded on the AE form with the following information:

- Description of the event
- Dates of onset and resolution
- Severity
- Action taken
- Outcome
- Relationship to investigational product
- Whether the AE is serious or not

Expectedness of an SAE will be defined based on whether the specificity or severity of which is not consistent with the current investigator brochure.

Other: The investigator may also need to consider whether an event is attributable to the investigational product, based on insufficiencies or inadequacies in the instructions for use or as a result of user error. The investigator must contact the Sponsor should this occur.

